13.1.2. Treatment Relatedness

Following (ICH-E3), the drug relatedness will be dichotomized as follows:

Drug related: at least possibly drug related, OR with missing drug relatedness (= worst-case)

Not drug related: less than possibly drug related.

In tabulations this dichotomized parameter will be used, but in the listings the original parameter will be presented.

13.1.3. Worst-Case Principle

When cross-tabulating AE preferred terms versus an AE attribute (e.g., intensity), the worst-case is always applied within each analysis period. I.e., when a subject has multiple times the same AE preferred term in the same analysis period, then the subject is reported only once: only with the worst intensity. If this happens in two different analysis periods, the AE is reported twice: once in each analysis period.

13.1.4. Adverse Event Onset Day and Duration

AE onset day in the study

$= ((\text{AE start date}) - (\text{date of first study drug administration})) + 1$, when the AE start date is completely known; the “+1” is not needed if the AE start date is before the first study drug administration date;

= missing when the AE start date is incomplete or unknown.

AE onset day in the period

= $((\text{AE start date}) - (\text{start date of the period into which the AE was allocated})) + 1$, when the AE start date is completely known;

= missing when the AE start date is incomplete or unknown.

AE duration

= $((\text{AE stop date}) - (\text{AE start date})) + 1$, when both dates are completely known;

= $((\text{Study termination date}) - (\text{AE start date})) + 1$, when the AE start date is fully known but the AE is not resolved at the end of the study; in this case the duration will be presented as “>x days” in the listing to identify it as a censored result;

= missing when the AE start date is incomplete or unknown, or when the AE has resolved but with an incomplete or unknown end date.

These derived parameters will only be presented in the listings. Note that the start and stop times of the AE are not used; only the dates are used.

13.1.5. Calculation of Percentages

All percentages will be calculated against the total number of subjects that are still in the study in that particular analysis period.

13.1.6. Tables

No formal inferential statistics (p-values) will be derived.

Analysis periods will be replaced by their respective treatment via the data captured in the CRF (i.e. an as-treated allocation). All tabulations and listings will present treatments rather than analysis periods.

Table 14.3.1.1: Treatment-emergent adverse events: Summary table

Tabulation per treatment of the number and percentage of subjects with the following:

- Subjects with at least one treatment-emergent adverse event (TEAE)
- Subjects with at least one serious TEAE
- Subjects who died
- Subjects with at least one mild TEAE as worst intensity
- Subjects with at least one moderate TEAE as worst intensity
- Subjects with at least one severe TEAE
- Subjects with at least one TEAE that was considered treatment-related
- Subjects with at least one TEAE for which the study treatment was temporarily stopped
- Subjects with at least one TEAE for which the study treatment was permanently stopped.

Population: safety population.

Table 14.3.1.2: Treatment-emergent adverse events: Tabulation of all adverse events

Tabulation of TEAE preferred terms per body class, per treatment group.

With a frequency tabulation of the number of events (reportings).

Population: safety.

Table 14.3.1.3: Treatment-emergent adverse events: Tabulation per intensity

Cross-tabulation of TEAE preferred terms versus their intensity. Use the worst-case intensity per TEAE per subject. Per treatment group.

Population: safety.

Table 14.3.1.4: Treatment-emergent adverse events: Tabulation of all treatment-related events

Tabulation of TEAE preferred terms per body class, per treatment group. Selecting only the TEAEs that were treatment-related (see section 13.1.2).

Population: safety.

Table 14.3.1.5: Treatment-emergent adverse events: Tabulation of the intensity of treatment-related events

Cross-tabulation per analysis period of TEAE preferred terms versus their intensity; per body class and per treatment group. Use the worst-case intensity per TEAE per subject, selecting only the TEAEs that were treatment-related (see section 13.1.2).

Population: safety.

Table 14.3.1.6: Serious treatment-emergent adverse events: Tabulation for EudraCT reporting

Tabulation of the number of subjects and events per body class, preferred term and per treatment.

Population: Safety.

Table 14.3.1.7: Non-serious treatment-emergent adverse events: Tabulation for EudraCT reporting

Same as the previous table, but only selecting TEAEs that are not serious.

Population: Safety.

Table 14.3.1.8: Non-serious treatment-emergent adverse events: Tabulation for EudraCT reporting of TEAEs occurring in at least 5% in one of the treatment group

Same as the previous table, selecting all the lines from the table where there is at least 5% occurrence in one of the treatment group either at SOC or at preferred term level. If the SOC line is selected but none of the associated preferred terms, then the SOC line is still to be presented but without preferred term lines.

Population: Safety.

13.1.7. Listings

Listing 16.2.10.1: Treatment-emergent adverse events: Summary listing of all events

Listing per treatment group, per subject of the following:

Period start and end date(time)

- AE preferred term (flagging serious TEAEs with an asterisk *)
- AE start and end date(time)
- AE onset day in study
- AE duration
- AE intensity
- AE drug relatedness
- AE action taken
- Concomitant therapy started (yes/no)

In such a way that all information fits on one line for each AE.

Periods without an AE will be included as “no AE” records.

Population: safety.

Listing 16.2.10.2: Treatment-emergent adverse events: Full listing

Listing per treatment group, per subject of all AE details, including MedDRA coding. Only actual adverse events will be presented here: periods or subjects without a TEAE will be left out. If a ConMed was started due to the AE, then the listing will present the ConMed's generic term.

Population: safety.

Listing 16.2.10.3: Pre-treatment adverse events: Full listing

Listing per treatment group and per subject of the screening period of all AE details, like in the previous listing.

Population: safety.

Listing 16.2.10.4: Adverse events: Full listing of the serious adverse events

Same as the previous listing, but only selecting SAEs (irrespective their treatment-emergence).

Population: safety.

Listing 16.2.10.5: Treatment-emergent adverse events: Full listing of the events leading to discontinuation

Same as the previous listing, but only selecting TEAEs that lead to a stop of study medication, or of the study itself.

Population: safety.

Listing 16.2.10.6: Adverse events: Coding information

Listing of all available coding steps between AE verbatim and AE system organ class, mentioning also the subjects who had this AE.

Population: safety.

13.2. LABORATORY SAFETY

13.2.1. Laboratory Units

The statistical analysis will only present results in Standard International (SI) units. Other units will not be presented.

Lab tests with only a very low sample size (N<3 overall) will not be presented in the tables, but only in the listings. Lab tests that are not part of the planned test panels according to the protocol will only be listed.

Urinalysis tests will be presented as part of the descriptive statistics and/or shift tables.

13.2.2. Number of Significant Digits

In tables and listings, the standardized results will be rounded to present only a relevant number of digits. The Mock TLFs contain tables on the expected number of significant digits per lab test. This rounding will be done prior to any parameter derivation.

Note that this table also contains the classification of lab tests into categories.

13.2.3. Baseline and Change from Baseline

The baseline is defined as the last sample prior to first dosing. Baseline will be determined per lab test individually. It is recognized that baseline tests may thus come from more than one lab sample.

The change from baseline will be calculated for all post-baseline time points as:

Change from baseline at time point t = value at time point t – baseline value.

13.2.4. Scoring of Laboratory Values and Urinalysis Results

All values will be compared to their matching normal ranges. The normal ranges provided by the laboratory will be used for this, as available in the database. Values are scored as abnormally low (L), normal (N) or abnormally high (H) by the central lab. The analysis will use this scoring (variable LBNRIND from SDTM.LB).

Tests without normal ranges will not be scored. Any clinical significance flags will be used in the listings.

13.2.5. Worst-Case Abnormality

Derived per parameter separately.

All nonmissing post-baseline values (including unscheduled measurements and follow-up measurements) will be used to derive the following worst-case:

- H = abnormally high:
at least one post-baseline measurement is above the normal range, and there are no values below the normal range.
- L = abnormally low:
at least one post-baseline measurement is below the normal range, and there are no values above the normal range.
- H+L = abnormally high and low:
at least one post-baseline measurement is above the normal range, and at least one other post-baseline measurement is below the normal range.
- N = normal:
all post-baseline measurements are within normal limits.

13.2.6. Tables

No formal inferential statistics (p-values) will be derived.

Table 14.3.2.1: Laboratory data: Descriptive statistics of the actual values per time point

Descriptive statistics of actual values per lab test category (hematology, biochemistry, urinalysis), lab test and unit, treatment group and time point.

Population: safety.

Table 14.3.2.2: Laboratory data: Descriptive statistics of the changes from baseline per time point

Descriptive statistics of changes from baseline (including 95% confidence interval of the mean change) per lab test category (hematology, biochemistry, urinalysis), lab test and unit, treatment group and time point. The actual value at baseline will also be presented in this table.

Population: safety.

Table 14.3.2.3: Laboratory data: Shift table according to the lab normal range per time point

Shift table per lab test category (hematology, biochemistry, urinalysis), lab test, treatment group and time point (including worst-case). The table will present the shift in abnormality (L/N/H) at each post-baseline time point versus the baseline abnormality (L/N/H). Tests without normal ranges will not be presented in this table.

Population: safety.

Table 14.3.2.4: Laboratory data: Treatment-emergent abnormalities per time point

Frequency table of the treatment-emergent lab abnormalities per lab test category (hematology, biochemistry, urinalysis), lab test, treatment group and time point (including worst-case). A post-baseline abnormality is considered treatment-emergent if it differs from the baseline result. Tests without normal ranges will not be presented in this table.

Population: safety.

Table 14.3.2.5: Laboratory data: Shift table of the categorical lab data per time point

Shift table per lab test category (hematology, biochemistry, urinalysis), lab test, treatment group and time point. Selecting only the tests with categorical data. The table will present the shift in value at each post-baseline time point versus the baseline value.

Population: safety.

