4.3. ALGORITHM OF ALLOCATING VISITS TO TIME WINDOWS

All visits (including unscheduled visits but excluding visits without data) will be placed into time windows according to their relative day (DY) in the study, according to the following allocation table:

Visits falling really late in the study will be allocated to a “>Day 29” interval, and will not be shown in tables nor figures, but will only be listed.

Time point label	Target day	Interval lower bound	Interval upper bound
Screening ³	NAP ⁴	NAP ⁴	NAP ⁴
Baseline ¹	NAP ⁴	NAP ⁴	NAP ⁴
Day 1 post-dose ³	NAP ⁴	NAP ⁴	NAP ⁴
Day 15	15	2	21
Day 29	29	22	36
>Day 29 ²	NAP ⁴	37	$+\infty$
Follow-up ³	11-17 days after last visit	NAP ⁴	NAP ⁴

¹ The actual baseline reference value will be determined per parameter as the last available pre-dosing data point, so might differ from this “baseline” visit interval.

² Visits falling really late in the study (relative day > 36; excluding the follow-up visit) will be allocated to a “>Day 29” interval, and will not be shown in tables nor figures, but will only be listed.

³ For the screening, day1 post-dose (vital signs) and follow-up visits, no time window is defined. The visit as recorded in the CRF will be used.

⁴ NAP = Not applicable

For efficacy, PD data, all by-time-point summaries will be based on the visit indicated on the subject’s CRF and will not be placed in time windows.

Tables, figures and listings will present the time points, not the visits.

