4.4. SELECTION OF VISITS

It is possible that more than one visit gets allocated into the same time window. In that case, only one visit will be selected for analysis tables and figures. The nonselected visit(s) will only be listed, and flagged as use=no.

The visit with a relative day (DY) closest to the target day will be selected. If there are multiple visits at the same distance of the scheduled visit day (meaning: equal ABS(DY – target day)), then the one latest in time is selected.

In case of multiple screening visits, the last pre-baseline screening measurement (the last visit happening before the scheduled 'Day 1 predose') is selected for analysis. This value (not the original first screening value) was also used in the clinical center to include the subject in the study.

In case more than one parameter is measured per time point (e.g. for lab), the selection is performed per parameter and per time point, not per “sample” and per time point. Missing values are removed before the selection is made.

As baseline reference point, the last nonmissing pre-dosing value will be used. This is normally the scheduled baseline itself. A missing scheduled baseline value will be imputed with the last nonmissing value of a preceding pre-dosing visit. This can be a screening visit or an unscheduled visit prior to the first dose of study medication. If there is an unscheduled measurement taken after the scheduled baseline, before the first dose of study drug, then this unscheduled measurement will be used instead of the scheduled baseline. If there is an

unscheduled measurement at the same datetime as the scheduled baseline, then it is assumed that the unscheduled measurement is taken after the scheduled baseline.

In case the screening visit is used to impute the baseline, the original screening visit as well as the imputed baseline will be presented in the tables. In the listings, only original screening data will be shown: the original screening visit will be shown and flagged as “reference” visit. The imputed baseline will not be shown.

In case an unscheduled visit is used to impute the baseline, the visit will be renamed to “baseline”. The imputed baseline will be presented in the tables. In the listings, the original unscheduled data will be shown and flagged as “reference” visit.

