8.4.2. Analysis

Table 14.1.3.1: Demographic data: Descriptive statistics

Continuous parameters: descriptive statistics per treatment group (and overall).

Categorical parameters: frequency tabulation per treatment group (and overall).

No formal comparison between the treatment groups is planned.

Population: the table will show

- safety
- ITT.

Table 14.1.3.2: Demographic data: Sub-group analyses: Descriptive statistics

The following sub-groups will be shown:

- By target C_{trough} at Day 15
- By target C_{trough} at Day 29
- By target C_{trough} at Day 15 and 29
- By sweat chloride (from arm with greatest volume) at baseline
- By sweat chloride (mean value from both arms) at baseline
- By %FEV1 at baseline

Population: the table will show

- safety
- ITT.

Table 14.1.3.3: Demographic data: Pooled analyses: Descriptive statistics

The following sub-groups will be shown:

- By target C_{trough} at Day 15
- By target C_{trough} at Day 29
- By target C_{trough} at Day 15 and 29

Population: the table will show

- safety
- ITT.

Listing 16.2.4.1: Demographic data

Listing per treatment group and per subject of all demographic parameters.

Population: safety.

Table 14.1.3.4: Baseline laboratory data: Tabulation of normal range

Frequency tabulation per lab test of the baseline result, categorized as low/normal/high according to the normal ranges (see section 13.2.4).

Population: Safety.

Table 14.1.3.5: Baseline ECG data: Tabulation of the normal range

Frequency tabulation per parameter (QT, QTcF) of the baseline result, categorized as (same as in section 13.3.4):

- ≤ 450 ms
- $]450,480]$ ms
- $]480,500]$ ms
- > 500 ms

Population: Safety.

Table 14.1.3.6: Baseline vital signs data: Tabulation of the normal range

Frequency tabulation per parameter of the baseline result, categorized as low/normal/high according to the normal ranges (see section 13.4.3).

Population: Safety.

Table 14.1.3.7: Baseline physical examination: Tabulation of the normal range

Frequency tabulation per CRF body system of the baseline result, categorized as normal/abnormal.

Population: Safety.

Table 14.1.3.8: Baseline pulse oximetry data: Tabulation of the normal range

Frequency tabulation per parameter of the baseline result, categorized as low/normal according to the normal ranges (see section 13.5.3).

Population: Safety.

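### For a liver test already above ULN at baseline, the SAP's treatment-emergent rule scores a rise past the Protocol 5.2.7 multiples as 0 on that test's line

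*SAP*

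**What the plan says.** On scoring, SAP 13.2.4 states: "Values are scored as abnormally low (L), normal (N) or abnormally high (H) by the central lab". It also says of the ranges: "The normal ranges provided by the laboratory will be used for this, as available in the database".

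SAP 13.2.6 builds two tables on that scoring. For Table 14.3.2.3: "The table will present the shift in abnormality (L/N/H) at each post-baseline time point versus the baseline abnormality (L/N/H"). For Table 14.3.2.4: "A post-baseline abnormality is considered treatment-emergent if it differs from the baseline result". The baseline result is not defined there, but SAP 8.4.2 describes Table 14.1.3.4 as "Frequency tabulation per lab test of the baseline result, categorized as low/normal/high according to the normal ranges".

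The worst-case row (SAP 13.2.5) draws on more data: "All nonmissing post-baseline values (including unscheduled measurements and follow-up measurements) will be used to derive the following worst-case". Its classes are still only H, L, H+L and N.

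For the by-time-point tables, SAP 4.3 to 4.5 place unscheduled visits in windows (Day 15: relative days 2 to 21; Day 29: 22 to 36) and keep the visit closest to the target day. For the rest: "The nonselected visit(s) will only be listed, and flagged as use=no".

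On the protocol side, exclusion 17 bars AST, ALT, ALP or GGT at or above 3 × ULN and bilirubin at or above 1.5 × ULN at screening. The liver criteria in Protocol 5.2.7 use >3 and >5 × ULN for AST/ALT, >2 × ULN for bilirubin and >3 × ULN for ALP/GGT.

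For QT and QTcF, SAP 13.3.4 and 13.3.6 use graded bands, change categories and a rule that requires the later result to be higher than baseline.

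**The concern.** Safety is the primary endpoint, and the laboratory data are summarized descriptively without p-values, so the by-arm tables are the comparison. A rule with one class above ULN cannot separate a stable mild elevation from a large rise in a subject who entered above ULN: both fall in the H/H cell and neither is counted as emergent. The same rule does count a trivial crossing of ULN.

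The numeric summaries do not always make up for this. A peak at a repeat visit that is not the selected visit in its window reaches the tables only through the worst-case row, which has the same three-level scoring.

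**Working it through.** No stated figure is involved, so the check applies the written rule to illustrative values in multiples of ULN. The thresholds are the protocol's; the subject values are examples.

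**Rule.** Class = H if value > 1 × ULN. Emergent = 1 if the later class is abnormal and differs from the baseline class, otherwise 0.

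| Test and change (× ULN) | Classes | Emergent |
|---|---|---|
| ALT 0.99 to 1.01 | N to H | 1 |
| ALT 0.8 to 5.1 | N to H | 1 |
| ALT 1.1 to 5.1 | H to H | 0 |
| ALT 2.9 to 5.1 | H to H | 0 |
| ALT 1.5 to 3.1 | H to H | 0 |
| Bilirubin 1.2 to 2.1 | H to H | 0 |
| GGT 2.0 to 3.1 | H to H | 0 |
| Bilirubin 0.8 to 2.1 | N to H | 1 |
| GGT 0.9 to 3.1 | N to H | 1 |

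On a grid of baselines 1.01 to 2.99 and later values 3.01 to 20, 0 of 199 × 200 = 39,800 pairs are emergent. With baselines at or below 1, all 50 × 200 = 10,000 are. The worst-case row gives the same answer, because worst-case H against baseline H is no difference.

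The last two table rows show the limit: the zero belongs to each test that starts above ULN. In the combined criteria, a partner test that was normal at baseline still counts 1 on its own line.

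**The other reading.** If the comparison is with the baseline number, ALT 2.9 to 1.2 is H and differs from 2.9, so it counts 1 although it improved. The category reading fits SAP 13.2.4, the shift table and Table 14.1.3.4 better, but the wording miscounts either way.

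**Visit selection.** Baseline ALT 2, bilirubin 1.4. Day 15 visit: 4 and 1.4. Repeat visit on day 18: 6 and 2.5. Early discontinuation visit on day 20: 5 and 2.2. All three lie in the window 2 to 21. Distances from the target are |15 − 15| = 0, |18 − 15| = 3 and |20 − 15| = 5, so day 15 is selected. The change table for Day 15 uses ALT 4 − 2 = +2.0 and bilirubin 1.4 − 1.4 = 0.0. The bilirubin of 2.5 is in no numeric table. The emergent count is 0 for both tests at Day 15 and in the worst-case row.

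**Size.** Planned active arm: 25 × 2/5 = 10. Pooled placebo: 2 × 25 × 1/5 = 10. One uncounted subject is 1/10 = 10 percentage points of that test's worst-case row.

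The documents do not give the share of subjects entering above ULN. Assuming 10% to 40% for a given test, 5 to 20 of 50 subjects would have a line that cannot register a further rise. The chance that an arm of 10 has at least one is 1 − 0.9^10 = 65% to 1 − 0.6^10 = 99%. This is exposure to the blind spot, not a forecast of liver events.

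**The case against.** The SAP delivers what Protocol 7.3.4 asks for, namely descriptive statistics and shifts by normal range; QT bands do not oblige ULN bands for laboratory tests. That stands: the SAP does not contradict the protocol, and the graded tables are an addition.

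Other outputs also carry the information. The laboratory profile plots put all subjects of an arm on one plot per test and include unscheduled results. The listings give values with normal ranges and clinical relevance flags. Clinically relevant abnormalities should be reported as adverse events, and Tables 14.3.1.1 to 14.3.1.5 count those by arm, including events for which treatment was permanently stopped. So it would be wrong to infer that arms can be compared only by reading listings subject by subject. But the adverse event route depends on investigator reporting, and none of these outputs is specified as a count by arm at the ULN multiples.

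Two further inferences are tempting and not supported:

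- **A subject who meets 5.2.7 disappears from the emergent table.** Only if every test involved was above ULN at baseline.
- **The peak at the mandatory retest is lost.** Protocol 5.2.7 requires retesting once one of its listed conditions is detected. A first visit with ALT 4 and bilirubin 1.4 × ULN, as in the example, does not clearly trigger that. Where a scheduled visit does trigger it, that visit already carries threshold-level values and, if selected, enters the numeric tables. A higher repeat value could still be only listed.

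The mock tables and the data safety monitoring board outputs are separate documents that I have not seen.

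**Conclusion.** The point holds per test. For any liver test above ULN at baseline, a rise past the 5.2.7 multiples scores 0 on that test's line at every time point and in the worst case, and is indistinguishable from no change in the shift table. This follows from the stated rule and rests only on the category reading of the baseline result; the numeric reading fails differently, by counting improvements.

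The gap is a by-arm count in the laboratory tables, not loss of the data. Its practical size depends on how many subjects enter above ULN and then rise, which the documents do not give; each such subject is 10 percentage points of a planned arm's row for that test. It is a cheap improvement to the reporting of the primary endpoint, worth making before database lock.

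**What to change.** In SAP 13.2.6, state for Table 14.3.2.4 that the baseline result means the baseline category.

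For AST, ALT, ALP, GGT and total bilirubin, add a worst-case post-baseline table and a baseline-to-worst shift table, both including unscheduled and follow-up values. Use reporting bands in multiples of ULN at the cut-offs already in Protocol 5.2.7:

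- AST and ALT: ≤1, >1 to 3, >3 to 5, >5
- ALP and GGT: ≤1, >1 to 3, >3
- Total bilirubin: ≤1, >1 to 2, >2

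Count any move to a band higher than baseline as emergent, following the directional rule the SAP uses for QT. In the example, ALT moves from >1 to 3 up to >5 and bilirubin from >1 to 2 up to >2, so both count. Exclusion 17 applies at screening but baseline is the last pre-dose sample, so a Day 1 value may already exceed 3 × ULN; say that such a subject counts only on moving to a still higher band.

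The cost is SAP wording and two tables. No new data or visits are needed, because the normal ranges are in the database. The bands change no clinical rule. They work test by test, so they do not count subjects who meet the combined, sequential 5.2.7 criteria. Worsening within a band stays uncounted: ALT 1.1 to 2.9 × ULN scores 0, while 2.9 to 3.1 scores 1.
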